### **3.1.1 Crossover Option in the Event of Unblinding**

At the time of study unblinding and in the event of a positive study result, all subjects currently receiving placebo will have the opportunity to receive active therapy with apalutamide (refer to Appendix 10).

### **3.1.2 Selection of the Primary Endpoint**

Men with high risk NM-CRPC, characterized by rapidly rising PSA in the absence of detectable metastases despite castrate levels of testosterone, are at significant risk for development of metastases and prostate cancer-specific death. As verified in a recently completed Phase III trial of denosumab, men with NM-CRPC who are at high risk for development of bone metastasis have a median overall survival of 44.8 months and a median bone-metastasis-free survival of 25.2 months (placebo arm). To date there are no approved treatments or standard of care for men with high risk NM-CRPC and thus this patient population represents an area of unmet medical need.

In consideration of the relatively long median OS (~49 months) in this population and the opportunity to assess for the development of distant metastasis as a clinically important milestone, metastasis-free survival (MFS) was chosen as the primary objective of this study. Metastasis from prostate cancer, especially bone metastases, is the source of prostate cancer specific morbidity and mortality. In addition, it triggers the need for a change in therapy that can be associated with an increase in morbidity (e.g., toxicity associated with chemotherapy), and in some cases leading to a change in quality of life for that patient.

Delaying the emergence of radiographically detectable distant metastasis, or prolongation of MFS as proposed, is a clinically relevant outcome that can be robustly and reliably assessed for determination of the true impact of a treatment on the NM-CRPC disease. In a high risk cohort of patients with biochemical recurrence after radical prostatectomy and a PSADT < 15 months, metastatic prostate cancer was reported to account for an estimated 90% of all deaths it is therefore conceivable that delaying the development of metastases would likely translate to delaying prostate cancer-specific death. The proposed MFS definition incorporates not only time to (bone or soft tissue) distant metastasis but also time to death and thus MFS can be a reasonable correlate to overall survival. Of note, based on retrospective landmark analyses at 3 and 5 years from the Radiation Therapy and Oncology Group 92-02 randomized trial in patients with locally advanced prostate cancer who had been treated with ADT and external beam radiation therapy, distant metastasis has been shown to be consistent with all four of Prentice's criteria for being a potential surrogate endpoint for prostate cancer-specific survival at 10 years.

## 3.2 STUDY OUTCOMES

### 3.2.1 Primary Endpoint

- Metastasis-Free Survival (MFS)

### 3.2.2 Secondary Endpoints

- OS
- Time to symptomatic progression
- Time to initiation of cytotoxic chemotherapy
- PFS
- TTM

### 3.2.3 Other Evaluations

- Health-related quality of life and prostate cancer-specific symptoms
- Type, incidence, severity, timing, seriousness, and relatedness of adverse events and laboratory abnormalities
- PSA response
- Time to PSA progression
- Population PK
- Exploratory biomarkers
- Assessment of ventricular repolarization
- Second progression-free survival (PFS2)
- Medical Resource Utilization (MRU)

## 4. PATIENT SELECTION

This study can only fulfill its objectives if appropriate patients are enrolled. The following eligibility criteria are designed to select patients for whom protocol treatment is considered appropriate. All relevant medical and non-medical conditions should be taken into consideration when deciding whether this protocol is suitable for a particular patient. It is expected that all patients will be treated according to local standard of care, including radiation therapy if needed for local disease, prior to enrolling.

No waivers will be granted for eligibility criteria deviations.

Patients considered screen failures may be subsequently rescreened. Rescreening must be discussed with and approved by the Sponsor on a case-by-case basis. Patients who are determined to be eligible for the study after rescreening must sign a new informed consent form (ICF) and be assigned a new patient number.

Treatment criteria for placebo subjects who crossover to active treatment with apalutamide (in the event of a positive study result and unblinding) are described in Appendix 10.

#### 4.1 INCLUSION CRITERIA

1. Criterion modified per Amendment INT-3

1.1 Criterion modified per Amendment INT-5

1.2 Histologically or cytologically confirmed adenocarcinoma of the prostate without neuroendocrine differentiation or small cell features, with high risk for development of metastases, defined as PSADT  $\leq$  10 months. PSADT is calculated using at least 3 PSA values obtained during continuous ADT (see Section 5.1).

2. Criterion modified per Amendment INT-5

2.1 Castration-resistant prostate cancer demonstrated during continuous ADT, defined as 3 PSA rises at least 1 week apart, with the last PSA  $>2$  ng/mL

3. Criterion modified per Amendment INT-3

3.1 Criterion modified per Amendment INT-6

3.2 Surgically or medically castrated, with testosterone levels of  $<50$  ng/dL. If the patient is medically castrated, continuous dosing with GnRHa must have been initiated at least 4 weeks prior to randomization and must be continued throughout the study to maintain castrate levels of testosterone.

4. Criterion modified per Amendment INT-3

4.1 Patients receiving bone loss prevention treatment with bone-sparing agents indicated for the treatment of osteoporosis at doses and dosing schedule appropriate for the treatment of osteoporosis (e.g., denosumab [Prolia®], zoledronic acid [Reclast®]) must be on stable doses for at least 4 weeks prior to randomization.

5. Criterion modified per Amendment INT-3

5.1 Criterion modified per Amendment INT-5

5.2 Patients who received a first generation anti-androgen (e.g., bicalutamide, flutamide, nilutamide) must have at least a 4-week washout prior to randomization AND must show continuing disease (PSA) progression (an increase in PSA) after washout.

6. Criterion modified per Amendment INT-3

6.1 Criterion modified per Amendment INT-5

6.2 At least 4 weeks must have elapsed from the use of 5- $\alpha$  reductase inhibitors (e.g., dutasteride, finasteride), estrogens (irrespective of dose used), and any other anti-cancer

therapy prior to randomization, including chemotherapy given in the adjuvant/neoadjuvant setting (e.g., clinical trial)

7. At least 4 weeks must have elapsed from major surgery or radiation therapy prior to randomization
8. Age  $\geq$  18 years
9. Eastern Cooperative Oncology Group (ECOG) Performance Status grade 0 or 1
10. Resolution of all acute toxic effects of prior therapy or surgical procedure to Grade 1 or baseline prior to randomization
11. Criterion modified per Amendment INT-3
  - 11.1 Criterion modified per Amendment INT-6
  - 11.2 Adequate organ function as defined by the following criteria:
    - Serum aspartate transaminase (AST; serum glutamic oxaloacetic transaminase [SGOT]) and serum alanine transaminase (ALT; serum glutamic pyruvic transaminase [SGPT])  $\leq$  2.5 x upper limit of normal (ULN)
    - Total serum bilirubin  $\leq$  1.5 x ULN. Total serum bilirubin  $>$  1.5 x ULN is allowed if Gilbert's disease is documented prior to end of screening procedures.
    - Serum creatinine  $\leq$  2 x ULN
    - Absolute neutrophil count (ANC)  $\geq$  1500/ $\mu$ L
    - Platelets  $\geq$  100,000/ $\mu$ L
    - Hemoglobin  $\geq$  9.0 g/dL
      - Administration of growth factors or blood transfusions will not be allowed within 4 weeks of the hematology labs required to confirm eligibility
12. Signed and dated informed consent document indicating that the patient (or legally acceptable representative) has been informed of all pertinent aspects of the trial prior to randomization
13. Criterion modified per Amendment INT-6
  - 13.1 Criterion modified per Amendment 7
  - 13.2 Willingness and ability to comply with scheduled visits, treatment plans, laboratory and radiographic assessments, and other study procedures, including ability to swallow study drug tablets, the completion of patient reported outcomes questionnaires and long-term follow-up

## 4.2 EXCLUSION CRITERIA

1. Criterion modified per Amendment INT-3
  - 1.1 Presence of distant metastases confirmed by blinded independent central review (BICR), including CNS and vertebral or meningeal involvement, or history of distant metastases. Exception: Pelvic lymph nodes <2 cm in short axis (N1) located below the iliac bifurcation are allowed
2. Symptomatic loco-regional disease requiring medical intervention, such as moderate or severe urinary obstruction or hydronephrosis, due to primary tumor (e.g., tumor obstruction of bladder trigone)
3. Prior treatment with second generation anti-androgens (e.g., enzalutamide)
4. Criterion modified per Amendment INT-5
  - 4.1 Prior treatment with CYP17 inhibitors (e.g., abiraterone acetate, orteronel, galeterone, ketoconazole, aminoglutethimide)
5. Prior treatment with radiopharmaceutical agents (e.g., Strontium-89), immunotherapy (e.g., sipuleucel-T), or any other investigational agent for NM-CRPC
6. Prior chemotherapy for prostate cancer, except if administered in the adjuvant/neoadjuvant setting
7. History of seizure or condition that may pre-dispose to seizure (e.g., prior stroke within 1 year prior to randomization, brain arteriovenous malformation, Schwannoma, meningioma, or other benign CNS or meningeal disease which may require treatment with surgery or radiation therapy)
8. Criterion modified per Amendment INT-3
  - 8.1 Criterion modified per Amendment INT-6
  - 8.2 Concurrent therapy with any of the following (all must have been discontinued or substituted for at least 4 weeks prior to randomization):
    - Medications known to lower the seizure threshold (for a complete list please see [Appendix 5](#))
    - Herbal (eg, saw palmetto) and non-herbal (eg, pomegranate) products that may decrease PSA levels
    - Systemic (oral/IV/IM) corticosteroids. Short term use ( $\leq 4$  weeks) of corticosteroids during the study is allowed if clinically indicated, but it should be tapered off as soon as possible
    - Any other experimental treatment on another clinical trial

- Agents indicated for the prevention of skeletal-related events in patients with solid tumors (e.g., denosumab [Xgeva®])
9. Criterion modified per Amendment INT-3
- 9.1 Criterion modified per Amendment INT-6
- 9.2 History or evidence of any of the following conditions:
- Any prior malignancy (other than adequately treated basal cell or squamous cell skin cancer, superficial bladder cancer, or any other cancer in situ currently in complete remission) within 5 years prior to randomization
  - Any of the following within 6 months prior to randomization: Severe/unstable angina, myocardial infarction, symptomatic congestive heart failure, arterial or venous thromboembolic events (e.g., pulmonary embolism, cerebrovascular accident including transient ischemic attacks), or clinically significant ventricular arrhythmias
  - Uncontrolled hypertension (systolic blood pressure  $\geq 160$  mmHg or diastolic BP  $\geq 100$  mmHg). Patients with a history of uncontrolled hypertension are allowed provided blood pressure is controlled by anti-hypertensive treatment.
  - Gastrointestinal disorder affecting absorption
  - Active infection, such as human immunodeficiency virus (HIV)
  - Any other condition that, in the opinion of the Investigator, would impair the patient's ability to comply with study procedures.

## 5. STUDY TREATMENTS

### 5.1 RANDOMIZATION CRITERIA

After patients have provided their written informed consent, completed all Screening assessments and received confirmation of eligibility, they will be randomized into the study using an Interactive Voice Randomization System (IVRS) and stratified based on:

- PSADT: > 6 months vs. ≤6 months
- Bone-sparing agent use: Yes vs. No
- Loco-regional disease: N0 vs. N1

In order to ensure accurate and consistent determination of PSADT across all sites, the IVRS will also provide PSADT calculations (using a linear regression model of the normal logarithm of PSA and time) based on at least 3 PSA values obtained during continuous ADT. All available consecutive PSA values obtained within 24 months prior to randomization beginning with the earliest value chosen for the PSADT calculation must be entered in the IVRS. The first and last PSA values used in the calculation must be separated by at least 8 weeks.

Those same PSA values should be used during Screening to determine whether the patient is eligible for the study (inclusion criterion #1.2). In order to pre-screen patients for possible enrollment into the study, PSADT can be calculated using the Memorial Sloan-Kettering Cancer Center (MSKCC) PSA Doubling Time prediction tool, available at the following website:

<http://nomograms.mskcc.org/Prostate/PsaDoublingTime.aspx>

### 5.2 BLINDING

Due to the objectives of the study, the identity of test and control treatments will not be known to investigators, research staff, or patients.

Only selected individuals not affiliated with the protocol will be unblinded to individual patient treatment assignment during the trial for the purposes of efficacy analyses and safety review. The randomization codes and all data sets will be stored in a secure area accessible only to these individuals, and only released on completion of the study and after the study database has been locked.

In emergency situations for reasons of patient safety (e.g., a serious unexpected/unlisted drug-related event; a medical emergency; a potentially life-threatening drug interaction), the blinding code may need to be broken. In those cases, whenever possible, a request for unblinding should be discussed with the Sponsor (or designee) prior to unblinding. Detailed instructions on the method for breaking the blind will be provided during site training and in the Investigator Site File.

## 5.3 FORMULATION

### 5.3.1 Apalutamide/Matched Placebo

The apalutamide tablet supplied for this study contains 60 mg of JNJ-56021927. It will be manufactured and provided under the responsibility of the Sponsor. Refer to the Investigator's Brochure for a list of excipients. Placebo will be provided as a tablet formulation and will be matched in size, color, and shape to active study drug in order to maintain the study blind.

### 5.3.2 Packaging, Storage, and Labeling

The apalutamide 60-mg tablets will be packaged in 120-count, 160 cc high-density polyethylene (HDPE) bottles with (b) (4). Bottles will include desiccant.

The study drug will be periodically tested and monitored for its acceptable shelf life for at least the duration of the study. Any study drug that fails to comply with the manufactured specifications will be promptly removed from the clinical study site and replaced with new supplies by the Sponsor (or designee).

Each bottle of study drug will be labeled with the required regulatory agency warning statement, the protocol number, the Sponsor's name, and directions for patient use and storage. The Investigator will ensure that the study drug is stored in appropriate conditions in a secure location with controlled access. For clinical formulation-specific and batch-specific storage instructions, see the packaging label.

### 5.3.3 Drug Administration

Apalutamide/matched placebo tablets will be administered orally on a continuous daily dosing regimen at a dose of 240 mg per day (4 x 60-mg tablets) with or without food.

### 5.3.4 Cycle Management

For the purposes of the study, a treatment cycle will consist of 4 weeks (28 days).

It is anticipated that individual patients may occasionally forget to take a dose. In those cases, missed doses should only be replaced if the patient remembers within a 12-hour window. After that, patients should just take the next dose the following day, without compensating for the missed dose (including vomited doses). In the event of dose delays due to transient toxicity, tumor assessments should remain on schedule independent of cycle length.

### 5.3.5 Dose Modifications

Inpatient dose interruptions and/or reductions will be permitted provided that study discontinuation criteria have not been met (please see Section 10).

- Patients experiencing treatment-related seizure of any grade will have study drug permanently discontinued.

- For patients experiencing Grades 1-2 treatment-related adverse events, short treatment breaks can be instituted as per the discretion of the Investigator until the severity of the toxicity decreases to Grade 1 or returns to baseline. If toxicity recurs, dose reductions to the next lower dose level will be allowed as per the discretion of the Investigator.
- For patients experiencing Grade  $\geq 3$  treatment-related adverse events other than seizure, study drug should be held until the severity of the toxicity decreases to Grade 1 or returns to baseline. If toxicity recurs at Grade 3 or higher, the dose of apalutamide should be reduced to the next lower dose level. A maximum of 2 dose level reductions will be allowed (Table 1).
- Any patient requiring > 28 days delay in treatment due to AEs may meet one of the criteria for study treatment discontinuation (see Section 10), which must be discussed with Sponsor.

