### 6.1 PROHIBITED MEDICATIONS AND TREATMENTS

As a class effect, androgen receptor antagonists have been associated with seizures due to an off-target mechanism of action (GABAA inhibition). In preclinical studies, at very high doses, dogs treated with apalutamide had tremors and generalized seizures. Patients will be closely monitored for seizures, but as a precautionary measure, drugs known to decrease the seizure threshold and/or cause seizure will be prohibited while on study. A list of these medications can be found in [Appendix 5](#).

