#### 9.1.4 Attribution

A suspected adverse reaction means any adverse event for which there is reasonable possibility that the study drug caused the adverse event. For the purposes of IND safety reporting, “reasonable possibility” means there is evidence to suggest a causal relationship between the drug and the adverse event.

The Investigator will assign attribution of the possible association of the event with the study drug using the following definitions:

- **Unrelated to study drug:** The adverse event is *clearly not related* or is *doubtfully related* to the study drug
- **Related to study drug:** The adverse event *may be related*, is *likely related*, or is *clearly related* to the study drug

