## 10. END OF TREATMENT

A patient may be discontinued from study treatment at any time if the patient, the Investigator, or the Sponsor feels that it is not in the patient's best interest to continue on study. If a patient's study treatment must be discontinued, this will not result in automatic withdrawal of the patient from the study.

The following is a list of possible reasons for early discontinuation of study treatment:

- Disease progression (*patients should be highly encouraged to stay on study treatment until there is BICR-confirmed radiographic progression; treatment decisions should not be based on PSA alone*)
- Any episode of seizure
- Any other adverse event that cannot be adequately managed with dose modifications, including dose interruption for  $\geq 28$  days may require study drug discontinuation, which must be discussed with the Sponsor.
- Protocol violation requiring discontinuation of study treatment
- Patient is not compliant with study procedures
- Lost to follow-up
- Patient withdrawal of consent

- Sponsor request for early termination of study

All patients discontinuing study treatment will enter the Long-term Follow-up Phase and will be followed for the development of symptomatic progression and initiation of subsequent anti-cancer therapies every 4 months until death, loss of follow-up, or withdrawal of consent, whichever comes first.

If a patient is lost to follow-up, every reasonable effort must be made by the study site personnel to contact the patient and determine the reason for discontinuation/withdrawal. The measures taken to follow up must be documented.

When a subject withdraws before completing the study, the reason for withdrawal is to be documented in the CRF and in the source document. Study drug assigned to the withdrawn subject may not be assigned to another subject. Subjects who withdraw will not be replaced.

Data to be collected for the end of treatment visit are described in Section 8.7. Patients will be followed for at least 28 days after the last dose of study drug. If a patient is withdrawn from treatment due to an adverse event, the patient will be followed until the adverse event has resolved or stabilized as per Section 9.2.

For information on subsequent therapy with abiraterone acetate see Section 8.10

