**APPENDIX 10: CROSSOVER TO OPEN LABEL APALUTAMIDE AFTER STUDY UNBLINDING**

At the time the decision is made to unblind the study, investigators will be notified by the sponsor. Subjects randomized to placebo who are currently on study treatment will be offered treatment with open-label apalutamide at 240 mg/day.

Subjects previously randomized to apalutamide will continue on protocol and follow the current schedule of activities (Appendix 1, with modifications below) and will be given open-label apalutamide.

For subjects who crossover from placebo to apalutamide, radiographic scans will no longer be required for the study and submitted for blinded central independent review. Subjects will be followed for progression per Investigator decision including symptoms, radiographic scans or PSA. PSA data submitted to the central laboratory will no longer be blinded. In addition, for all subjects, PK samples will no longer need to be collected at the time of unblinding.

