**Discontinuation Criteria for Subjects Who Crossover**

Subjects who discontinue open label apalutamide will continue in Long-Term Follow-up per Section 8.9.

If a subject meets criteria as defined in Section 10 of the protocol, apalutamide must be discontinued.

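### For a seizure judged unrelated to study drug, Sections 5.3.5 and 10 and Appendix 10 of the protocol do not agree on whether treatment must stop

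*Protocol*

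**What the plan says.** Three places in the current protocol text bear on stopping treatment after a seizure.

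- **Section 5.3.5 (Dose Modifications):** "Patients experiencing treatment-related seizure of any grade will have study drug permanently discontinued". This is compulsory and applies at every grade, but only to seizures judged related. The section opens by saying that dose interruptions and reductions "will be permitted provided that study discontinuation criteria have not been met (please see Section 10", so it treats the Section 10 list as criteria.
- **Section 10 (End of Treatment):** the list includes "Any episode of seizure", with no condition on cause. Its lead-in reads: "The following is a list of possible reasons for early discontinuation of study treatment".
- **Appendix 10 (discontinuation criteria for crossover):** "If a subject meets criteria as defined in Section 10 of the protocol, apalutamide must be discontinued". Seizure is not named; it is reached only through the reference to Section 10.

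Two further provisions matter. Under Section 9.1.4, "The Investigator will assign attribution of the possible association of the event with the study drug", and the choice is binary: a doubtful link counts as unrelated and a possible link as related. Under Appendix 10, after unblinding, "Subjects previously randomized to apalutamide will continue on protocol and follow the current schedule of activities", with open-label drug. The compulsory sentence sits under the heading for patients who cross over, that is, those first randomized to placebo.

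**The concern.** The protocol treats seizure as a recognised risk. Section 6.1 says that "androgen receptor antagonists have been associated with seizures due to an off-target mechanism of action", Section 1.1.2 reports convulsions in dogs at high doses, Section 4.2 excludes men with a seizure history or predisposing condition, and Appendix 5 prohibits drugs that lower the seizure threshold. For such an event, sites need to know whether study drug must be stopped. The texts differ on two questions: whether the cause of the seizure matters, and whether stopping is compulsory.

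Two things are at stake. One is that the same event could lead to different decisions at different sites, or for different patients at one site. The other is a safety table. SAP Section 7.6.1 tabulates adverse events that led to discontinuation of study drug, using the end-of-treatment reason and the action recorded on the adverse event form. If sites act differently on an unrelated seizure because they read the text differently, that enters the table.

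**Working it through.** No sample size, alpha or event count is involved, so the check is to apply the texts to each case.

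| Case | Section 5.3.5 | Section 10 | Appendix 10 crossover sentence | Result |
|---|---|---|---|---|
| Related seizure, main study (blinded, or original apalutamide patient after unblinding) | Must stop | Listed as a possible reason | Does not apply | Stop |
| Related seizure, crossover patient | Must stop | Listed | Must stop, through Section 10 | Stop |
| Unrelated seizure, main study (blinded, or original apalutamide patient after unblinding) | Silent | Listed as a possible reason | Does not apply | Not fixed |
| Unrelated seizure, crossover patient | Silent | Listed | Must stop, through Section 10 | Stop |

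1. Rows one and two agree. For a related seizure the texts, read together, lead to the same place.
2. Rows three and four differ for the same event. In row three a site can treat the Section 10 item as a criterion that has been met, because Section 5.3.5 calls the list criteria. Another site can rely on the Section 10 lead-in and continue treatment. Both follow the protocol.
3. After unblinding, rows three and four are in force at the same time. Former placebo patients who cross over are under row four and patients first randomized to apalutamide are under row three, all on open-label apalutamide. The planned randomization (800 apalutamide, 400 placebo) gives ceilings on these groups; the real numbers would be smaller, because only men still on treatment are concerned and crossover has eligibility criteria.
4. The row a main-study patient falls in depends on the investigator's attribution. Because a doubtful link is classed as unrelated, a doubtful seizure falls in row three.
5. The Appendix 10 sentence reaches further than seizure. Section 10 says that an interruption of 28 days or more may require discontinuation after discussion with the sponsor. The crossover sentence, read literally, makes that item compulsory too. The root of the problem is therefore the status of the Section 10 list, together with the relatedness limit in Section 5.3.5.

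**The case against.** The strongest reply is that the texts can be read together. Section 5.3.5 deals largely with treatment-related toxicity, so its silence on unrelated seizure is natural, and it sends the reader to Section 10. Both it and Appendix 10 call the Section 10 list criteria. The seizure item carries no qualifier, whereas the adverse event item beside it says where discretion applies. The list also includes loss to follow-up and withdrawal of consent, so its lead-in may be loose drafting and not a grant of discretion. This is a fair reading, but the lead-in does not compel it, and a site that takes the lead-in at its word is not in breach.

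The reply also limits the practical effect, and that part stands. A possible link counts as related and sites are told of the class effect, so many seizures may be attributed to study drug. Section 9.1.2 gives convulsions as an example of a serious event, and serious events reach the sponsor within 24 hours. Attribution under blinding is ordinary in a double-blind trial and is no defect here.

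A reader might infer more than the documents support:

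- **That there are three separate seizure rules.** Only Sections 5.3.5 and 10 name seizure in their stopping text; the Appendix 10 sentence is a general cross-reference.
- **That seizure in general lacks a stopping rule.** Related seizure leads to stopping throughout.
- **That seizure narratives would depend on how sites read the text.** SAP Section 7.6.1 requires a narrative for every patient with a seizure, listed separately from those who discontinue, and SAP Appendix 3 defines seizure by a fixed list of terms.
- **That seizure is the main neurological risk.** The documents treat it as a recognised risk and do not rank it.
- **That the primary analysis is threatened.** Efficacy is analysed by intention to treat, and patients who stop before progression continue imaging every 16 weeks under Section 8.9.

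**Conclusion.** The point holds for a seizure judged not related to treatment. In that case the main-study wording leaves the outcome open and the crossover wording requires stopping, and after unblinding the two can apply to men on the same drug at the same time.

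The number affected is probably small. The documents give no expected seizure rate, and Section 1.1.3 reports no seizures at any dose level among the 30 Phase I patients. The effect is confined to consistency of a safety decision and to counts of adverse events leading to discontinuation. The conclusion assumes that sites apply the wording as written and that no separate site instruction, which the documents do not show, already settles the matter. It takes no position on which stopping rule is clinically right.

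**What to change.** Reconcile Section 5.3.5, Section 10 and the crossover discontinuation text in Appendix 10. One statement should answer two questions:

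1. Does the investigator's judgement of relatedness affect what happens after a seizure?
2. Are the Section 10 items criteria that compel stopping, or possible reasons for it? If they are mixed, mark each item.

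The answer should apply in the same way to patients in the blinded phase, original apalutamide patients on open-label drug and crossover patients, and the other two places should refer to it. The choice of rule belongs to the sponsor's clinical team.

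The cost is protocol wording in three places and a notice to sites. No analysis, sample size or data collection changes.
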